## 5 STUDY ENROLLMENT AND WITHDRAWAL

### 5.1 Subject Inclusion Criteria

Individuals aged  $\geq$  18 years presenting to the Emergency Department with “likely upper GI bleed” (typically bloody emesis and/or coffee ground vomiting and/or melena) that has occurred within the previous 48 hours.

### 5.2 Subject Exclusion Criteria

1. Upper GI Bleed with hemodynamic instability (BP<90 mmHg, pulse>120 beats per minute, and Hgb < 9 g/dL)
2. High Risk Upper GI Bleed (Glasgow Blatchford Score\*  $\geq$  6)
3. Signs, symptoms or history of liver cirrhosis or liver failure
4. Signs, symptoms or history of decompensated heart failure or congestive heart failure
5. Presumed Pregnant, trying to conceive or breastfeeding
6. Known history of gastric cancer
7. Known history of gastric or esophageal varices
8. GI surgery within the last 6 months
9. Prior enrollment in the CHEER Study
10. Prisoner or Ward of State
11. Trouble swallowing, suspected bowel obstruction or perforation, per treating clinician
12. Past UGI tract surgery (e.g., Bilroth I or II, esophagectomy, gastrectomy, bariatric procedure) that changes Gastrointestinal anatomy
13. Known history of gastroparesis, esophageal stricture or Crohn’s disease
14. Altered mental status that limits the ability to swallow a capsule
15. Expected to have Magnetic Resonance Imaging (MRI) examination within 7 days
16. Consumed medications within the past 12 hours that may coat the upper GI tract such as antacids or sucralfate or Maalox and potentially limits capsule visualization
17. Patient either refuses or is unable to get traditional EGD
18. Patient does not have reliable contact information – no phone, no permanent address
19. Patient refuses
20. Unable to provide written consent
21. Non-English speaker
22. Suspected middle or lower GI bleeding
23. Treating ED Physician is not amenable to admission or discharge based on randomization or Video Capsule Endoscopy results.

\* As a modification, the GBS Score modified from the traditional GBS score to reduce the Hemoglobin cut-off for 6 points from 10g/dL to 9 g/dL (see Appendix B, CHEER 4; patient screening)

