## PROTOCOL SUMMARY

Title:	Capsule Endoscopy for HEmorrhage in the ER (CHEER)
Précis:	This is a multi-center randomized controlled trial examining the use of Video Capsule Endoscopy (VCE) to discharge low-moderate risk patients with suspected upper gastrointestinal bleeds (UGIB) from the Emergency Department (ED.) We will enroll 100 subjects at 4 sites who present with signs of hemodynamically stable UGIBs and compare VCE risk assessment to an Active Control (AC) group who receive inpatient upper endoscopy (EGD).
Objectives:	
Primary: Our primary goal is to determine whether ED VCE is able to discharge low risk patients for outpatient management of upper GI bleeds.
 
Secondary: Our secondary objective is to estimate the sensitivity and specificity of VCE compared to subsequent EGD in the detection of serious bleeding lesions in the upper gastrointestinal (GI) tract.
 
Sample size is 100 patients, age <math>\geq</math> 18 in 4 urban EDs, mixed gender, mixed race, hemodynamically stable with possible co-morbidities.

Population:	Study subjects will be enrolled from larger pool of adult ED patients presenting with acute overt UGIB defined as bloody emesis and/or coffee ground vomiting and/or melena within the previous 48 hours.
Number of Sites:	4
Study Duration:	12 months
Subject Participation Duration:	30 days
Estimated Time to Complete Enrollment:	1 year

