**4.4 Study procedure:**

1. Screen potential patients with signs of upper GI bleeding (melena, h/o hematemesis or coffee-ground emesis) from general pool of ED patients. (Form used, *CHEER:1*)
2. Patients who screen as eligible will be approached about potential interest, to review of inclusion and exclusion criteria, and obtain informed consent. (*See below for full list of inclusion/ exclusion criteria.*)
3. Research Coordinator will calculate traditional risk stratification scores (Glasgow – Blatchford and Rockall).
4. All consented patients will be given a study ID and recorded in enrollment log. (Form used, *CHEER:2*)
5. Once enrolled, all subjects will be randomized to either Active Control (AC) [admission plus EGD within hospital stay] or experimental Capsule Endoscopy Risk Assessment (CERA) in ED.
6. Only patients randomized to the experimental arm will receive video capsule endoscopy in the emergency department. 20 to 60 minutes before capsule ingestion, each patient in the experimental arm receives a single dose of intravenous metoclopramide 10 mg (or erythromycin 500mg intravenously if there is a contraindication), which helps to promote gastric motility and improves visualization of the gastric mucosa at endoscopy. The Research Coordinator (RC) will prepare the patient for VCE. (*See below for description of procedure.*)
7. Within 2 hours of presenting to the ED, patient will ingest video capsule-- RC will monitor progress on real-time viewer for passage through pylorus. Upon passing the pylorus, we will record 5 more minutes of video or until battery runs out – whichever occurs first.
8. Patient data will be completed using a standardized data collection tool including the following elements: chief complaint of patient, history of present illness, past medical history, pertinent lab findings, current medications, vital signs, focused physical exam findings and all relevant treatments administered during the ED and hospital stay. (Form Used, *CHEER:3*)

9. At completion of VCE, patient satisfaction regarding VCE will be assessed in patients in the experimental group. (Form used, *CHEER*: 4)
10. For Active Control (AC) group each patient will be admitted.

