During hospital admission, EGD will be performed on all subjects and hemostasis therapy applied as necessary. The study team decided against mandating that EGD be performed within 24 hours of hospital admission. This is a pragmatic trial. The longer the duration between the inpatient EGD and the ED VCE the greater the likelihood of discrepancy in the findings that may be due to a change in the lesion as part of its natural course or due to treatments delivered. However, the primary objective of the study is not to evaluate diagnostic accuracy of the ED VCE. The study team decided it was more important to enroll subjects in a timely manner than exclude subjects because the inpatient EGD was not completed within 24 hours.

For the experimental CERA group, subjects will be monitored for a minimum of 4 hours after ingestion. VCE will be undergo a formal review after completion of the VCE by a staff gastroenterologist with extensive experience in VCEs of the small bowel, colon, and esophagus. Both research personnel and the gastroenterologist will undergo a capsule training program organized by Medtronic and receive accreditation after the training.

11. Subjects in the experimental arm who have no sign of active bleeding, show no serious endoscopic findings on capsule, and have stable hemoglobin, blood pressure and heart rate for at least 4 hours will be discharged from the ED. Discharged CE patients will be scheduled to have an outpatient EGD within 3 days post discharge. Patients will be instructed to return to the ED sooner if signs of new bleeding develops. The Research Coordinator will facilitate setting up this appointment for the patient.

Any subject in the experimental arm with a positive VCE or a negative VCE but has a drop in Hemoglobin  $\geq 3$  at 4 hours or an elevated HR or low BP will be admitted. A hemoglobin drop between 2 and 3 will NOT automatically transfer patient to active control arm. In these cases, decision to proceed will be up to discretion of treating physician. We anticipate that all admitted patients in the experimental arm will undergo EGD in the hospital (same as AC arm.)

12. Primary Outcome: (1) Percent Discharged Home. Assumption is that 100% of Active Control / standard risk assessment will be admitted.
13. Secondary Outcome: Sensitivity and specificity of VCE compared to EGD

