**4. Upper GI Bleed with hemodynamic instability (BP<90 mmHg, pulse>120 beats per minute, and Hgb<9 g/dL)**

Yes No (Must be NO to be eligible for study) 5. High Risk Upper GI Bleed (Glasgow Blatchford Score  $\geq$  6)

Yes No (Must be NO to be eligible for study) **5. Presumed pregnant, trying to conceive or breastfeeding**

Yes No (Must be NO to be eligible for study)

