**Hemoglobin (g/dl)**

>13.0 (0 points for either gender)

12.0-13.0 (1 point male 0 point female)

9.0-12.0 (3 points male 1 point female)

< 9.0(6 points for either gender)

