**Systolic blood pressure (mmHg)**

>110 (0 points)

100-109 (1 point)

90-99 (2 points)

< 90 (3 points)

**Heart rate higher than 100 bpm** Yes (1 point) No (0 points)

**Presentation with syncope** Yes (2 points) No (0 points)

**Cardiac Disease (echocardiography evidence)** Yes (2 points) No (0 points)

**Hepatic disease (chronic, acute liver disease)** Yes (2 points) No (0 points)

**Presentation with melena** Yes (1 point) No (0 points)

GBS Score \_\_\_\_\_

(NOTE: GBS <6 to be eligible for the study)

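### Exclusion 1 joins its three limits with 'and', so it removes nobody beyond the GBS limit and lets some patients with SBP <90 and pulse >120 pass the numeric criteria; implanted devices are not screened for

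*Combined protocol and SAP*

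**What the plan says.** Section 5.2, item 1, excludes "Upper GI Bleed with hemodynamic instability (BP<90 mmHg, pulse>120 beats per minute, and Hgb < 9 g/dL"). Item 4 of the screening form (18.4) has the same limits with the same conjunction, "BP<90 mmHg, pulse>120 beats per minute, and Hgb<9 g/dL", as a single Yes/No item. Item 2 of 5.2 excludes a modified GBS of 6 or more.

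The scoring form (18.6) gives haemoglobin "< 9.0(6 points for either gender"). Systolic pressure below 90 scores 3. The only heart-rate item is "Heart rate higher than 100 bpm", worth 1 point however fast the pulse.

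The Protocol Summary describes subjects with "signs of hemodynamically stable UGIBs".

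In section 4.4, item 6 says "each patient in the experimental arm receives a single dose of intravenous metoclopramide 10 mg" (erythromycin if contraindicated), and item 7 says "Within 2 hours of presenting to the ED, patient will ingest video capsule". Under item 11, capsule-arm subjects without active bleeding or serious capsule findings who "have stable hemoglobin, blood pressure and heart rate for at least 4 hours will be discharged from the ED". The same item admits a subject with a negative capsule whose heart rate is raised or blood pressure low.

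On implanted devices, section 2.3.1 says that people with pacemakers or similar devices will not receive the capsule. Section 2.1 says these devices are not a contraindication with newer capsules. None of the 23 exclusions in 5.2 and no item in 18.4 mentions them, and the medical-history checklist in 18.5 does not ask.

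**The concern.** An exclusion for haemodynamic instability should keep out patients who are hypotensive or markedly tachycardic. With the limits joined by 'and', it applies only when low pressure, fast pulse and low haemoglobin occur together, and the GBS limit already removes everyone in that group. The question is then whether the GBS limit alone keeps unstable patients out.

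If it does not, the harm falls at enrolment. An unstable patient can be randomised and, in the capsule arm (CERA), receive the prokinetic and the capsule before the stability rule applies. If still unstable, that subject is admitted whatever the capsule shows, which lowers percent discharged, the primary outcome. Sites that read the item literally and sites that read it as 'any of' would also enrol different populations.

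The device gap has a different effect. A subject with a pacemaker can be randomised to CERA and then denied the capsule. That is non-adherence in one arm only, and section 4.4 states no disposition for a CERA subject with no capsule result.

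**Working it through.** **Inputs.** Points come from the form in 18.6. BP in exclusion 1 is taken as systolic, as on that form.

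- Systolic pressure: >110 = 0; 100–109 = 1; 90–99 = 2; <90 = 3.
- Heart rate above 100 = 1.
- Haemoglobin, men: >13 = 0; 12–13 = 1; 9–12 = 3; <9 = 6.
- Haemoglobin, women: >13 = 0; 12–13 = 0; 9–12 = 1; <9 = 6.
- Blood urea: <18.2 = 0; then 2, 3, 4 and 6 for the higher bands.
- Syncope, cardiac disease and hepatic disease = 2 each; melena = 1.
- Eligible if the total is below 6.

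**Step 1: does exclusion 1 remove anyone whom exclusion 2 does not?** Meeting all three limits gives at least 3 (pressure) + 1 (pulse) + 6 (haemoglobin) = 10, which is above the limit. Over all 7,680 combinations on the form (heart rate split at 100 and 120), the number excluded by item 1 alone is 0.

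**Step 2: can a patient with low pressure and fast pulse be eligible?** These two signs score 3 + 1 = 4, so at most 1 further point is allowed. That forces urea below 18.2, no syncope, and no cardiac or hepatic points. Haemoglobin and melena together may add 0 or 1:

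- Men: haemoglobin >13 with or without melena (2 patterns), or 12–13 without melena (1), giving 3.
- Women: >13 with or without melena (2), 12–13 with or without melena (2), or 9–12 without melena (1), giving 5.

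The total is 3 + 5 = 8. For example, a man with systolic pressure 85, pulse 125, haemoglobin 14, urea below 18.2 and melena scores 3 + 1 + 0 + 0 + 1 = 5. He passes both items.

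**Step 3: each sign separately.** With haemoglobin of 9 or more and no cardiac or hepatic points, each vital-sign pattern has 2 sexes × 5 urea bands × 3 haemoglobin bands × 2 melena × 2 syncope = 120 score patterns.

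| Vital signs | Base points | Eligible patterns of 120 |
|---|---|---|
| SBP <90 and pulse >120 | 4 | 8 |
| SBP <90 and pulse ≤100 | 3 | 16 |
| Pulse >120 and SBP 90–99 | 3 | 16 |
| Pulse >120 and SBP 100–109 | 2 | 30 |
| Pulse >120 and SBP >110 | 1 | 46 |

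**Step 4: effect of 'any of'.** Of the 7,680 combinations, 594 are eligible under the present wording. An 'any of' rule would exclude 187 of them, including all 8 from step 2. All 187 come from the pressure and pulse limits, because haemoglobin below 9 already scores 6.

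**Step 5: effect on percent discharged.** The documents give no allocation ratio. Assuming 1:1 (50 in CERA), one subject who must be admitted regardless of the capsule takes up to 1/50 = 2.0 percentage points off percent discharged in that arm. Assuming 2:1 (67 in CERA), it is 1/67 = 1.5 points.

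**Step 6: devices.** No arithmetic applies. Section 2.3.1 withholds the capsule, section 2.1 says there is no contraindication, and 5.2, 18.4 and 18.5 do not ask. As written, a device carrier can reach randomisation undetected. If the device is then found, 2.3.1 bars the capsule.

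**The case against.** The best defence is that no clinician would read the item literally. Its operative words are haemodynamic instability, the parenthesis is a loosely punctuated list, and the specimen row of the screening log (18.3) gives that label alone as the failure reason. A screener who sees a pressure of 85 and a pulse of 125 has good reason to answer Yes. 'Any of' is probably what was meant. Other safeguards also exist: exclusion 23 lets the treating physician decline, section 2.3.1 bars enrolment that may interfere with standard care, and item 11 of 4.4 blocks discharge of an unstable capsule-arm subject.

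These points limit the practical harm, and unsafe discharge is well guarded. None sets a vital-sign limit before randomisation, and the stated definition still contradicts its label. Research staff complete a form whose only guidance is the literal list.

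The effect on the primary outcome is also open to challenge, and much of that challenge stands. Admission for unstable vital signs is part of the CERA strategy, and it biases against the trial's hypothesis. At an assumed 40 low-risk subjects per arm (1:1, 20% high-risk), power for 100% versus 75% admission is about 94%, so a few such subjects would not threaten the comparison. This effect is secondary to the enrolment problem. The documents also describe no specific hazard of the prokinetic or capsule in a hypotensive patient.

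Score patterns carry no frequencies, and the single-sign counts are failures only if 'any of' is intended. Both points are correct.

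On devices, 2.3.1 can be read as the study rule and 2.1 as background, and a subject without a capsule does not meet the discharge conditions. Exclusion 4 and the cardiac points may catch some device carriers. The rule is still absent from both lists, and no disposition is stated.

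**Conclusion.** The concern holds. As worded, exclusion 1 excludes nobody whom exclusion 2 does not (minimum GBS 10). A patient with systolic pressure below 90 and pulse above 120 can be eligible by the numeric criteria, in 8 of 120 score patterns. This contradicts the item's own label and the Protocol Summary. It rests on reading BP as systolic and 'and' literally. How many patients would be affected cannot be estimated from the documents and could be none. The figure of 1.5 to 2.0 percentage points per subject rests on an assumed allocation ratio and is a secondary consequence.

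The conflict over implanted devices is real and separate: the rule in 2.3.1 has no screening step behind it, and 2.1 contradicts it. Both points should be fixed. The main reasons are safety at enrolment and consistent screening across sites.

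**What to change.** In 5.2 item 1 and 18.4 item 4, define instability as *any of: systolic BP <90 mmHg; pulse >120 beats per minute; Hgb <9 g/dL*. The clinical lead should confirm this before the amendment is issued, because it also excludes isolated tachycardia.

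For devices, decide which statement governs. Either add *pacemaker or other implanted electronic device* to 5.2 and the screening form, or delete the sentence in 2.3.1 that withholds the capsule. Either way, nobody should be randomised to CERA and then denied the capsule.

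The cost is amendment wording in 5.2 and 18.4, plus 2.3.1 if that sentence is deleted, and some additional screen failures whose number the documents do not allow to be estimated.

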### 5.3 Strategies for Recruitment and Retention

Patients will be screened and recruited through the Emergency Department. Research assistants will be monitoring chief complaints and then reviewing the patient record, interview with provider and patients for inclusion and exclusion criteria.

## **5.4 Subject Withdrawal**

### **5.4.1 Reasons for Withdrawal**

A subject can withdraw at any time and for any reason. Subject should provide written notice to PI as to withdrawal intent. The PI can withdraw a patient from the study for noncompliance issues or serious medical conflicts.

### **5.4.2 Handling of Subject Withdrawals**

[figure not shown]
If subject withdraws from the study, no further contact will be attempted or made by study staff. If patient is withdrawn from study by PI for non-compliance or health related concerns, study staff will notify subject via phone call and/or IRB approved letter if direct contact cannot be made.

## **5.5 Premature Termination or Suspension of Study**

Notification of all study subjects. No further data collection.

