Any major adverse events that occur will be reported directly to the principal investigator who will be available to study subjects 24 hours a day. Severe adverse events will be reported to the entire research team, the DSMB and to IRB within 24 hours. Updates will be provided after a full investigation is completed. Since the PillCam is an FDA-approved device and not an experimental device, all SAE's will also be reported to the FDA. Potential major adverse events include missed high-risk lesions, delayed definitive care, patients who are discharged from hospital and experience a major outcome (see below), capsule retention in the small bowel, and any serious outcome that may be related to study protocol. A DSMB will be formed that includes experts in emergency medicine, gastroenterology and research methodology. DSMB will meet annually during which a report will be produced by PI and as needed for SAE's.

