**Other Outcomes:**

1. Patient satisfaction with the VCE procedure. (Form Used: *CHEER #4*)

2. GI Physician Final Read and Site physician agreement of VCE results. (Form Used: *CHEER #5*)
3. Serious Adverse Events at Day 7 and Day 30 (Mortality, Re-Bleeding, Total Blood Transfusions, Surgery, Capsule-specific). (Form Used: *CHEER #7*)
4. ED Length of Stay (hours).
5. Hospital Length of Stay (days).
6. Cost-effective analysis.
  - At conclusion of study, we will construct a model using standard decision analysis software to examine the cost-effectiveness of three available strategies for a base-case patient who presents to the ED with either mild or moderate risk scenarios (by Glasgow-Blatchford Score) for requiring invasive hemostatic intervention (i.e., endoscopic, surgical, etc.) The three available diagnostic strategies are (1) direct imaging with video capsule endoscopy performed in the ED, (2) risk stratification using the Glasgow-Blatchford score, and, finally, (3) an admit-all strategy.

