14. Safety outcomes. Patient will be followed for clinical course and EGD results. Day 7 and Day 30, subject follow-up by telephone (if home) or in person (if still in hospital) to assess for adverse events or recurrent bleeding episode. (Form Used, *CHEER*: 6,7)
15. All VCE's will be re-read by offsite gastroenterologists who are blinded to the first interpretation and the patient.

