## **12 STUDY OVERSIGHT**

A Data Safety Monitoring Board (DSMB) consisting of appropriately qualified independent experts has been appointed by the PI to provide review of data on patient safety and study progress. The membership roster is maintained by Site PI and study coordinator and is available from them as needed. PI will provide reports including adverse events. A summary of DSMB deliberations will be prepared distributed to the subsites to submit to their IRB.

The Data and Safety Monitoring Board provides ongoing evaluation of the study progress including patient accrual and retention, monitoring of adverse events, and the adequacy and efficiency of the analysis plan to discern outcomes that might require study modifications, or result in early cessation of the study due to its benefits or harms. The DSMB does not evaluate the scientific merit or methodology of the study, nor does it directly participate in the execution of a study's protocol, monitor the budget, or approve sub-protocols or other modifications to the study.

The major responsibilities of the Board are:

- To review the data analysis plan and make recommendations for additions or changes to the plan.
- To assess the performance of each participating center and make appropriate recommendations regarding continuation, probationary status, or termination.
- To consider patient accrual, overall study progress (timeline and follow-up participation), adverse effects and patient safety, treatment effectiveness/futility, and proper monitoring and reporting by the study team as these affect the ethical treatment of participants or the ethical conduct of research.
- Report to the PI on any perceived problems with study conduct, enrollment, sample size, and data collection.

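### Section 5.5 ends all data collection if the study is stopped or suspended, cutting off the planned Day 7 and Day 30 safety contacts of subjects still inside their 30-day window

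*Combined protocol and SAP*

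**What the plan says.** Section 5.5, on premature termination or suspension, consists of two statements: subjects are to be told, and there is to be "No further data collection". It covers a temporary suspension as well as a final stop, and names no exception.

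Elsewhere the protocol relies on contact after the emergency department visit for its safety data:

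- Section 4.4 plans "Day 7 and Day 30, subject follow-up by telephone (if home) or in person (if still in hospital) to assess for adverse events". The same contacts are to pick up any new bleeding. Section 7.5 repeats the contacts on days 7 and 30.
- Section 3.2, under other outcomes, lists "Serious Adverse Events at Day 7 and Day 30 (Mortality, Re-Bleeding, Total Blood Transfusions, Surgery, Capsule-specific").
- Section 4.4 provides that capsule-arm subjects with no active bleeding or serious finding who "have stable hemoglobin, blood pressure and heart rate for at least 4 hours will be discharged from the ED". It adds: "Discharged CE patients will be scheduled to have an outpatient EGD within 3 days post discharge".
- Section 2.3.1 counts among potential major adverse events "patients who are discharged from hospital and experience a major outcome (see below), capsule retention in the small bowel". It also requires severe events to be reported within 24 hours, with updates once they have been fully investigated.
- Section 12 asks the DSMB to watch for outcomes that might "result in early cessation of the study due to its benefits or harms".

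**The concern.** The experimental step is to send home patients whose counterparts in the control arm are all admitted. Several of the harms the protocol names for that step, such as a major outcome after discharge or a retained capsule, can only appear once the subject has left. The Day 7 and Day 30 contacts are the planned way of finding them.

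The protocol foresees a stop for harm. Applied as written, Section 5.5 would then end follow-up of the most recently randomised subjects in both arms on the stopping date. Their Day 30 outcomes, and for some their Day 7 outcomes, would be missing because of the stop, and the stop may itself have been caused by the safety results. Missing data of that kind cannot be treated as unrelated to outcome, and they arise when the DSMB and the IRBs most need a complete safety account. A short suspension would have the same effect on anyone whose contact fell due during it.

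**Working it through.** The plan gives no figure on this point to reproduce. The check has two parts.

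**1. Does any other section keep follow-up going after a stop?**

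- Section 5.4.2 ends contact with subjects who withdraw. It does not cover subjects who have not withdrawn when the study stops.
- Section 7.6 collects adverse events while the protocol is being conducted and is silent on the period after a stop.
- Sections 10.2 and 10.3 deal with reporting of events, not with continued contact to find them.
- Section 2.3.1 provides for investigation of severe events that have been reported. It does not provide for scheduled contact with subjects who have reported nothing.
- Section 12 gives the DSMB its remit but no procedure for subjects in follow-up at a stop.

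No section preserves the Day 7 and Day 30 contacts, or collection of a pending EGD result, after a stop.

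**2. How many subjects would be affected?**

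Inputs from the protocol:

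- 100 subjects and one year to enrol (Protocol Summary; Section 6.2).
- Windows of 30 days, 7 days, and 3 days to the outpatient EGD (Section 4.4).
- Lower value for the share of the capsule arm discharged: 25%, the difference in admission rates used in Section 11.2. It is a detectable difference for low-risk lesions, used here only as a low value.
- Upper value: in the feasibility trial described in Section 2.1, 7 of 37 capsule patients were admitted, so 30/37 = 81% were not.

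Assumptions not in the documents: uniform accrual over 365 days, and 1:1 allocation.

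Formula: subjects inside a window at a stop = (100/365) × window in days. Halve this for the capsule arm, then multiply by 0.25 and by 0.81 for discharged capsule subjects.

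| Not yet reached | All subjects | Capsule arm | Discharged capsule subjects |
|---|---|---|---|
| Day 30 | 100 × 30/365 = 8.2 | 4.1 | 1.0 to 3.3 |
| Day 7 | 100 × 7/365 = 1.9 | 1.0 | 0.2 to 0.8 |
| Day 3 (EGD due) | 100 × 3/365 = 0.8 | 0.4 | 0.1 to 0.3 |

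The Day 3 row is informative mainly in its last column, because the 3-day limit applies to discharged capsule subjects.

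Share of those enrolled who would lack Day 30 data, by timing of the stop:

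- after 25 subjects: 8.2/25 = 33%
- after 50 subjects: 8.2/50 = 16%
- after 75 subjects: 8.2/75 = 11%

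The counts scale with the accrual rate. If 100 subjects took twice as long (730 days, for illustration), 100 × 30/730 = 4.1 would be short of Day 30.

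**The case against.** The strongest opposing case is that the consequences are limited, and much of it stands.

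- **The triggering events would not be lost.** A reader might infer that the signal behind a stop could no longer be checked. The documents do not support that. Under Section 2.3.1 severe events go to the research team, DSMB and IRB within 24 hours, with updates after investigation, and nothing there limits this to a running study. Section 5.5 does not say whether data collection includes such investigation, so the two sections need reconciling.
- **Few EGD results would be pending.** A reader might also infer that recent discharges would have no EGD data at all. The outpatient EGD is due within 3 days and follow-up for it is arranged before the subject leaves the emergency department (Section 7.1), so fewer than one discharged capsule subject is expected to be inside that window. Section 5.5 stops data collection, not care.
- **Subjects past Day 30 are unaffected.** The rule does not remove safety data for everyone ever given the capsule.
- **The primary outcome is untouched.** The percentage discharged home is fixed at the emergency department disposition. Day 7 and Day 30 events are listed under other outcomes.
- **A stop during enrolment may be unlikely.** No interim analysis or numerical boundary is given, and the DSMB meets annually and as needed for serious events (Section 2.3.1). Appendix A places its report in April 2019, when recruitment was due to end.
- **Accrual may be slower than planned.** The protocol is dated 9/27/19, after that planned end, and slower accrual puts fewer subjects in the window.

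None of this answers the central point. Investigating reported events is not the same as contacting subjects who have reported nothing, and ordinary care may reveal some events without the protocol providing for their collection. If a stop follows an unscheduled review of serious events, completing follow-up of recent subjects is what the reviewers would want.

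**Conclusion.** The point holds in a limited form. Section 5.5 states a rule that, followed as written, cuts short the routine safety follow-up of randomised subjects who are within 30 days and have not withdrawn. This conflicts with the protocol's own Day 7 and Day 30 safety outcomes and sits badly with its provision for investigating severe events. The resulting gap could be linked to the reason for stopping.

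The numbers are small in absolute terms: about 8 subjects at any one stop, of whom about 1 to 3 are discharged capsule subjects. They depend on the accrual, allocation and discharge assumptions shown above. As a share of those enrolled, the gap is largest for an early stop. The rule matters only if the study is stopped or suspended, and it does not bear on the primary analysis. It should still be changed, because a safety decision in a trial of this size may rest on few events and the correction costs little.

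**What to change.** In Section 5.5, replace "No further data collection" with a statement along these lines: on termination or suspension, enrolment stops; for every randomised subject in either arm who has not withdrawn consent, the Day 7 and Day 30 contacts, adverse-event reporting and collection of results from EGDs already scheduled are completed as planned.

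Add a cross-reference to Section 2.3.1 making clear that investigation of severe events continues after a stop. Section 5.4.2 can stay as it is, since it already respects withdrawal.

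The cost is a short amendment and at most about 30 days of contacts already planned, for about 8 people under the assumptions above. No treatment or discharge rule changes.
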